## 8.2. Statistical Analyses

*Natural log-transformed parameters ( $AUC_{inf}$ ,  $AUC_{last}$ , CCI) will be analyzed using a mixed effect model with treatment as a fixed effect and subject as a random effect. Estimates of the adjusted mean differences (Test-Reference) and corresponding 90% CIs will be obtained from the model. The adjusted mean differences and 90% CIs for the differences will be exponentiated to provide estimates of the ratio of adjusted geometric means (Test/Reference) and 90% CI for the ratios. The Test and Reference treatments to estimate the treatment difference for each of the study objectives are as follows:*

- *Objective 1: caffeine 100 mg (Period 1, Day 1) will be the Reference treatment; abrocitinib 200 mg + caffeine 100 mg (Period 2, Day 8) will be the Test treatment.*
- *Objective 2: efavirenz 50 mg (Period 1, Day 1) will be the Reference treatment; abrocitinib 200 mg + efavirenz 50 mg (Period 2, Day 8) will be the Test treatment.*
- *Objective 3: omeprazole 10 mg (Period 1, Day 1) will be the Reference treatment; abrocitinib 200 mg + omeprazole 10 mg (Period 2, Day 8) will be the Test treatment.*

*Residuals from the model will be examined for normality and the presence of outliers via visual inspection of plots of residuals vs predicted values and normal probability plots of residuals but these will not be included in the CSR. If there are major deviations from normality or outliers, then the effect of these on the conclusions will be investigated through alternative transformations and/or analyses excluding outliers. Justification for any alternative to the planned analysis will be given in the report of the study.*

**Table 3. PK Parameters to be Summarized Descriptively by Treatment**

Parameter	Summary Statistics
$AUC_{inf}$ , $AUC_{last}$ , CCI	N, arithmetic mean, median, cv%, standard deviation, minimum, maximum, geometric mean and geometric cv%.
CCI	
	CCI
	CCI
	CCI

*Box and whisker plots for individual participant parameters ( $AUC_{inf}$ ,  $AUC_{last}$ , CCI) will be presented by treatment and overlaid with geometric means.*

Supporting data from the estimation of **CCI**  $AUC_{inf}$  will be listed by analyte and treatment: terminal phase rate constant ( $k_{el}$ ); goodness of fit statistic from the log-linear regression ( $r^2$ ); the percent of  $AUC_{inf}$  based on extrapolation ( $AUC_{extrap\%}$ ); and the first, last, and number of time points used in the estimation of  $k_{el}$ . This data may be included in the clinical study report.

Presentations for *caffeine, efavirenz and omeprazole* concentrations will include:

- A listing of all concentrations sorted by participant ID, period and nominal time postdose. The concentration listing will also include the actual times. Deviations from the nominal time will be given in a separate listing.
- A summary of concentrations by treatment and nominal time postdose, where the set of statistics will include n, mean, median, standard deviation, coefficient of variation (cv), minimum, maximum and the number of concentrations above the lower limit of quantification.
- Median concentrations time plots (on both linear and semi-log scales) against nominal time postdose by treatment (all treatments on the same plot per scale, based on the summary of concentrations by treatment and time postdose).
- Mean concentrations time plots (on both linear and semi-log scales) against nominal time postdose by treatment (all treatments on the same plot per scale, based on the summary of concentrations by treatment and time postdose).
- Individual concentration time plots by treatment (on both linear and semi-log scales) against actual time postdose (there will be separate spaghetti plots for each treatment per scale).
- Individual concentration time plots by participant (on both linear and semi-log scales) against actual time postdose [there will be separate plots for each participant (containing all treatments) per scale].

For summary statistics, median and mean plots by sampling time, the nominal PK sampling time will be used, for individual participant plots by time, the actual PK sampling time will be used.

### **8.3. Safety Analysis**

A set of summary tables will be produced to evaluate any potential risk associated with the safety and toleration of administering abrocitinib when co administered with single doses of caffeine, efavirenz and omeprazole.

#### **8.3.1. Treatment and Disposition of Participants**

Participant evaluation groups will show end of study participant disposition and will show which participants were analyzed for pharmacokinetics, as well as for safety (adverse events

and laboratory data). Frequency counts will be supplied for participant discontinuation(s) by treatment.

Data will be reported in accordance with the sponsor reporting standards.

### **8.3.2. Demographic and Clinical Examination Data**

A breakdown of demographic data will be provided for age, race, weight, body mass index, and height. Each will be summarized by sex at birth and 'All Participants' in accordance with the sponsor reporting standards.

### **8.3.3. Discontinuation(s)**

Participant discontinuations, temporary discontinuations or dose reductions due to adverse events will be detailed and summarized by treatment.

Data will be reported in accordance with the sponsor reporting standards.

### **8.3.4. Adverse Events**

Adverse events will be reported in accordance with the sponsor reporting standards by treatment.

### **8.3.5. Laboratory Data**

Laboratory data will be listed in accordance with the sponsor reporting standards.

### **8.3.6. Vital Signs Data**

Vital Signs data will be databased and available upon request.

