1. PROTOCOL SUMMARY

1.1. Synopsis

Brief Title: A Phase 1 Study to Estimate the Effect of Multiple Dose Abrocitinib on the PK of Caffeine, Efavirenz, and Omeprazole in Healthy Adult Participants

Rationale

The purpose of the study is to evaluate the effect of abrocitinib on the in vivo PK of sensitive CYP1A2, 2B6 and 2C19 substrates, caffeine, efavirenz, and omeprazole, respectively.

Objectives and Endpoints

Objectives	Endpoints
Primary:	Primary:

To estimate effect of multiple dose abrocitinib on the PK of single, oral doses of caffeine, efavirenz and omeprazole in healthy participants.	
AUC_{inf} (if applicable, otherwise AUC_{last}) of caffeine, efavirenz and omeprazole.
Secondary:	Secondary:

To evaluate the safety and tolerability of abrocitinib when co administered with single doses of caffeine, efavirenz and omeprazole.	
Vital signs, laboratory tests and AEs.
CCI	

Overall Design

Brief Summary

This is a Phase 1, open-label, multiple dose, single fixed-sequence, 2-period study to evaluate the effect of abrocitinib on the PK of caffeine, efavirenz and omeprazole in healthy adult participants. A total of approximately 13 healthy male and/or female participants will be enrolled in the study to obtain at least 12 evaluable participants who complete the study. Participants who withdraw from the study or are considered non-evaluable may be replaced at the discretion of the sponsor.

Participants will be screened within 28 days of the first dose of study intervention. Participants will have a phone contact 3 days prior to Day 1 dosing (Day -3) in Period 1 as a reminder to abstain from caffeine-containing products. Participants will be admitted to the

CRU at least 24 hrs prior to Day 1 dosing (Day -1) in Period 1. Participants will remain in the CRU for a total of 15 days and 14 nights.

Participants will have a telephone contact between 28-35 calendar days after the last administration of the investigational product.

Number of Participants

A total of approximately 13 healthy male and/or female participants will be enrolled in the study to obtain at least 12 evaluable participants who complete the study.

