9. STATISTICAL CONSIDERATIONS

Detailed methodology for summary and statistical analyses of the data collected in this study is outlined here and further detailed in a SAP, which will be maintained by the sponsor. The SAP may modify what is outlined in the protocol where appropriate; however, any major modifications of the primary endpoint definitions or their analyses will also be reflected in a protocol amendment.

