9.3.2. Other Safety Analyses

All safety analyses will be performed on the safety population.

AEs, ECGs, BP, pulse rate, and safety laboratory data will be reviewed and summarized on an ongoing basis during the study to evaluate the safety of participants. Any clinical laboratory, ECG, BP, and pulse rate abnormalities of potential clinical concern will be described. Safety data will be presented in tabular and/or graphical format and summarized descriptively, where appropriate.

Medical history and physical examination and neurological examination information, as applicable, collected during the course of the study will be considered source data and will not be required to be reported, unless otherwise noted. However, any untoward findings identified on physical and/or neurological examinations conducted during the active collection period will be captured as AEs, if those findings meet the definition of an AE. Data collected at screening that are used for inclusion/exclusion criteria, such as laboratory data, ECGs, and vital signs, will be considered source data, and will not be required to be reported, unless otherwise noted. Demographic data collected at screening will be reported.

CCI

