### 6.2. Safety Endpoints

Any events occurring following start of treatment or increasing in severity will be counted as treatment emergent.

Events that occur in a non-treatment period (for example, Follow-up) will be counted as treatment emergent and attributed to the previous treatment taken.

The following data are considered in standard safety summaries (see protocol for collection days and list of parameters):

- *adverse events*,
- *laboratory data*.

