### 6.2.5. Other Safety Data

Additional safety data will be collected as described in the protocol and will be listed if collected in the sponsor's database.

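### Vital signs are one of three components of the secondary endpoint, but the SAP plans no output for them

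*SAP*

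**What the plan says.** The protocol states the secondary endpoint in the Synopsis and again in Section 3: "Vital signs, laboratory tests and AEs". It serves the objective of evaluating safety and tolerability when abrocitinib is given with the three probe drugs.

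Protocol 9.3.2 adds a reporting commitment: "Any clinical laboratory, ECG, BP, and pulse rate abnormalities of potential clinical concern will be described". A later sentence, on tabular or graphical presentation of safety data, applies only where appropriate. The quoted sentence carries no such qualifier.

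The SAP treats the three components differently:

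- **Adverse events** (SAP 8.3.4) are reported by treatment.
- **Laboratory tests** (SAP 8.3.5): "Laboratory data will be listed in accordance with the sponsor reporting standards".
- **Vital signs** (SAP 8.3.6): "Vital Signs data will be databased and available upon request".

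SAP 6.2 introduces a list with "The following data are considered in standard safety summaries", and the list holds two items, adverse events and laboratory data. SAP 8.3.1 describes the safety evaluation group by the same two data types. SAP 6.2.3 nevertheless defines a vital-signs baseline, one per study period, and SAP 6.2.4 does the same for ECG.

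**The concern.** Keeping data in a database is storage, not a planned presentation. If the programming team follows the SAP exactly, the study report will carry AE tables and a laboratory listing, and nothing on the third component of an endpoint that the protocol set for itself. A reader could not tell from the SAP whether this is a deliberate reduction or an oversight, because the SAP does not present it as a change from the protocol. The protocol's promise to describe BP and pulse rate abnormalities would also have no counterpart in the document that specifies the outputs.

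What is at stake is complete reporting of a secondary safety endpoint. The estimates of the interaction effect are not involved.

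**Working it through.** The documents give no figure to reproduce on this point. The check is a comparison of sections, followed by simple counts.

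**Step 1. Does any other SAP section supply a vital-signs output?**

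- SAP 6.2 (safety endpoints): the list contains AEs and laboratory data only. No.
- SAP 6.2.3 (vital signs): gives collection times by reference to the protocol, and a baseline definition. It names no output.
- SAP 6.2.5: "Additional safety data will be collected as described in the protocol and will be listed if collected". This sits under the heading for other safety data and concerns what is additional. Vital signs have their own sections (6.2.3 and 8.3.6), so the specific rule in 8.3.6 governs. No.
- SAP 8.3 (opening sentence): promises a set of safety summary tables in general terms without naming vital signs. Section 8.3.6 then settles how they are handled. No.
- SAP 8.3.1: identifies safety with AEs and laboratory data. No.
- SAP 8.3.8 (other safety data): none planned.

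Named components with a planned SAP output: AEs (1) + laboratory tests (1) + vital signs (0) = 2 of 3.

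**Step 2. How much data is affected?**

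The Schedule of Activities footnote places vital signs at screening, before dosing on Period 1 Day 1, and on Period 2 Day 11. Protocol 9.3.2 treats screening values used for eligibility as source data that need not be reported, so they are left out. Early-termination and unplanned recordings are also left out.

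- Planned on-study recordings per completer: 2.
- For 12 completers: 2 × 12 = 24 sets.
- If all 13 enrolled complete: 2 × 13 = 26 sets.
- Sets that appear in a planned SAP output: 0.

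**Step 3. Does the SAP baseline work if these data are reported?**

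SAP 6.2.3 and 6.2.4 take as baseline the final planned predose recording within each period. Abrocitinib is given on Period 2 Days 1 to 10. The only planned Period 2 recording of BP, pulse rate and ECG for a completer is on Day 11, after the last dose. Planned predose recordings of these measures in Period 2 therefore number 0, and 0 of 12 completers would have a Period 2 baseline under the rule. With the Period 1 Day 1 predose recording as baseline for the whole study, all 12 would have one, assuming it is taken as scheduled. Protocol 8.2.3 already uses that recording as the reference for ECG comparisons. The COVID-19 temperature checks during residence are a separate schedule row with no predose timing, so they do not supply this baseline.

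**The case against.** The strongest reply is that the two documents are meant to be read together and that the SAP is entitled to do less. Protocol Section 9 says "The SAP may modify what is outlined in the protocol where appropriate", and it requires an amendment only for major changes to the primary endpoint definitions or their analyses. The SAP is also consistent with itself: 6.2, 8.3.1 and 8.3.6 point the same way, and 8.3.7 handles ECG as 8.3.6 handles vital signs. That looks like chosen reduced reporting. The protocol's commitment to describe abnormalities is not withdrawn. With two recordings per completer, no concurrent control, no hypothesis and no decision rule, little would be learned from tables. Under protocol 10.3.1, vital-sign abnormalities that the investigator considers clinically significant are AEs, and AEs are reported by treatment.

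Most of this stands, and it fixes the size of the point. It does not close the gap. Permission to modify does not give a named endpoint component a result. The AE route covers only values that the investigator judges significant, and it reports a different component.

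A reader might also infer three stronger things that the documents do not support:

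- **That the SAP makes a prohibited departure.** Section 9 allows non-primary changes without an amendment.
- **That SAP 8.3.6 contradicts the sentence "AEs, ECGs, BP, pulse rate, and safety laboratory data will be reviewed and summarized on an ongoing basis during the study".** That sentence states its purpose as evaluating participants' safety, which describes review while the study runs. It does not commit to an output in the final report, so it is not a conflict.
- **That the baseline rule spoils a planned analysis.** No planned output uses it.

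**Conclusion.** The point holds as a SAP-to-protocol mismatch of small practical weight, and it should be corrected. The SAP as written gives no output for one of the three named components of the secondary endpoint, and it does not carry over the unqualified commitment in protocol 9.3.2 on BP and pulse rate abnormalities. The primary PK analysis is unaffected, and clinically significant abnormalities remain visible as AEs.

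The conclusion rests on reading SAP 8.3.6 as the governing rule for vital signs over the general wording in SAP 6.2.5 and 8.3. The counts assume completers with recordings taken as scheduled.

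Two limits apply. The baseline problem is real as text but affects only a change-from-baseline presentation, which is not planned. The endpoint argument does not extend to ECG, which is not a named component. It would also be too much to infer a human vital-sign signal from the nonclinical findings on heart rate, diastolic BP and body temperature in protocol 2.2.1 and 2.2.3. The Phase 2b summary in protocol 2.2.4.1 reports no clinically significant vital-sign findings. The case rests on the protocol's own endpoint.

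**What to change.** 1. Add vital signs to the list in SAP 6.2, and align the description of the safety evaluation group in SAP 8.3.1.
2. Replace SAP 8.3.6 with two outputs: a listing of the on-study BP, pulse rate and temperature recordings, parallel to the laboratory listing in 8.3.5; and a description of the BP and pulse rate abnormalities that protocol 9.3.2 covers. State the criteria in the SAP, or refer to a sponsor standard if it contains them. SAP 6.2.2 invokes sponsor criteria for laboratory tests only, so the existence of vital-sign criteria there should be confirmed and not assumed.
3. In the same edit, define baseline in SAP 6.2.3 and 6.2.4 as the Period 1 Day 1 predose recording for the whole study.

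A sentence declaring reduced reporting would make the choice visible, but it would still leave the component without a result, so it is not an adequate substitute.

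The cost is one extra listing, a short description and SAP wording, all from data already planned for collection. No new assessment, protocol amendment or change to the PK analysis is needed.

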### **8.3.7. ECG Data**

ECG data will be databased and available upon request.

### **8.3.8. Other Safety Data**

None.

### **8.3.9. Concomitant Treatments**

All concomitant medication(s) as well as non-drug treatment(s) will be provided in the listings.

### **8.3.10. Screening and Other Special Purpose Data**

If these data is brought in-house, then it will be listed.

## 10. APPENDICES

### Appendix 1. SAS CODE FOR ANALYSES

An example of the PROC MIXED code is provided below:

```
proc mixed data=tab.pk;
  by analyte;
  class trt participant;
  model l&var= trt/ ddfm=KR;
  random participant /participant=participant;
  lsmeans trt;
  estimate 'Combined single agents alone vs Coadministration with abrocitinib ' trt -1 1
/c1 alpha=0.1;
  ods 'Estimates' out=est&var;
  ods 'lsmeans' out=ls&var;
  ods 'covparms' out=cov&var;
  ods 'tests3' out=tst&var;
run;
```

/\* Letter assignments for treatments (trt) within the estimate statement above are as follows;

A = Combined single agents alone (caffeine, efavirenz, omeprazole (Reference));

B = Coadministration (caffeine, efavirenz, omeprazole with abrocitinib (Test));

\*/;
